5.4 Reporting Adverse Events

SAEs will be reported to the CDC and all participating IRBs according to institutional requirements.

If indicated, adverse events (AEs) will be reported to the CDC's Vaccine Adverse Event Reporting System (VAERS). The National Childhood Vaccine Injury Act requires healthcare providers to report:

- Any adverse event listed by the vaccine manufacturer as a contraindication to further doses of the vaccine; or
- Any adverse event listed in the [VAERS Table of Reportable Events Following Vaccination](#) [PDF - 75KB] that occurs within the specified time period after vaccination.

In addition, CDC encourages reporting of any clinically significant adverse event that occurs in a patient following a vaccination, even if there is uncertainty regarding if a vaccine caused the event.

5.5 Follow-up on days 3-14 for infants in the vaccinated group

**This period of time (day 3-14) will begin at 48 hours after vaccination.*

Infants in the vaccinated group will be followed for the above clinically important AEs, SAEs, and concomitant medications on days 3-14. If an infant in the vaccinated group is discharged or transferred prior to day 14 (with no EHR accessible), then these data will be obtained via follow-up phone call from the study staff to the parent/guardian.

5.6 Treatment Assignment Procedures

This is an open-label, prospective, randomized study for infants who are eligible to receive 2-month vaccinations. To the extent feasible, all infants randomized to the vaccinated group will be given the same type/brand of vaccines at all sites. Infants in the unvaccinated group will not receive any vaccine during the study.

5.6.1 Randomization

Participants will be randomized (1:1) to either vaccinated or unvaccinated groups using a permuted block randomization scheme stratified by gestational age (<28 weeks, ≥28 weeks) and study site (i.e. Duke University Medical Center, University of North Carolina at Chapel Hill)

Hospital, and Cincinnati Children's Hospital Medical Center). Randomization will occur within 6 hours of anticipated vaccination of infants in the vaccinated group, but infants will be allowed to receive vaccines up to 12 hours post-randomization. The first 12 infants enrolled in the Pilot Phase I will be randomized in a separate permuted block by manual randomization (e.g., envelopes). The project statistician at Duke University will generate permuted block randomization schemes, which will be uploaded to REDCap for the full study. The randomization schedule will not be available to the study staff, so the next randomization allocation will not be known before randomization occurs. Following confirmation of study eligibility criteria, participant randomization will be through REDCap with treatment allocation recorded on the case report form. In the event that REDCap is unavailable, manual randomization will occur through the use of envelopes. The project statistician will prepare 20 envelopes per site that will use the same randomization strategy as the primary scheme embedded in REDCap. When manually randomizing, the team member will pull the next envelope in order. In order to capture the allocation per subject, a separate form in REDCap will be used by the personnel to add the assignment. A log will need to be kept at the site capturing these instances.

5.6.2 Blinding

This study will be open label and study staff, caregivers, and parent(s)/LAR(s) will not be blinded to treatment arm assignments. The output from the cardiorespiratory monitors will be read by analysts who are blinded to the treatment arm assignments.

5.5.3 Vaccine Supply, Storage, and Administration

Vaccine Supply and Storage

Pharmacy-supplied US licensed vaccines will be administered to the vaccination group as part of this study. The following vaccine brands will be used for this study: PCV13 (Prevnar[®] 13, Pfizer); DTaP-IPV-HBV (Pediarix[®], GlaxoSmithKline); and Hib (ActHib[®], Sanofi Pasteur). However, given the potential for unforeseen manufacturing issues/specific product shortages, the use of alternate U.S.-licensed vaccines may be required.

Vaccine Administration

Only infants randomized to the vaccinated group will be vaccinated during the protocol specified observation period. A single administration of PCV13 and DTaP-HBV-IPV and Hib comprises intramuscular delivery of 0.5 mL total volume of each vaccine. For each infant, all vaccines will be administered simultaneously by licensed nurses within the study sites. Injections given in the same thigh should be separated by 1 inch or more, if possible, so that any local reactions can be differentiated. The research staff will record vaccine brand, lot numbers, dose, date/time and site of vaccine administration. For continuity of care purposes, documentation of vaccine administration will be done in a manner that the infant's healthcare provider can access.

After administration, used study syringes will be disposed of according to standard operating procedure.

Although oral rotavirus vaccine is recommended by the ACIP for infants at 2-months of age, this vaccine will not be administered during the study to prevent potential nosocomial spread of this live vaccine virus.

6 STATISTICAL CONSIDERATIONS

6.5 Sample Size and Power Estimation

Power considerations related to the primary objective

The study has approximately 84.3% power to reject the null hypothesis of no difference in the proportion of infants with apnea in the “vaccinated” group compared to the “unvaccinated” group based on a two-side alpha 0.05 chi-square test with N=135 per group. This assumes that the proportion of infants with apnea will be 15% in the “unvaccinated” group and 2-fold higher (30%) in the “vaccinated” group. This assumption is based on a review of the literature¹⁴ and expert opinion. The study allows for a 10% drop out rate to give a total sample of 300 infants.

During the pilot study, at least 12 infants will be enrolled to assess feasibility. Following completion of the pilot study, a total of at least 288 infants will be enrolled.

6.6 Analysis Plan

6.6.1 Pilot Study

The pilot phase of the study will include 12 infants. There will not be any formal analysis of study data. However, the feasibility benchmarks listed in **Table 5** will be documented for the first 12 patients to assess protocol adherence. These subjects will contribute to the final sample for analyses in the study objectives.

Table 5: Benchmarks for Pilot	
Benchmark	Target
Among pre-screened and eligible, LARs approached for consent	70%
Among approached for consent, consent obtained	40%
Documentation of reason for non-consent (of those approached)	80%
Among consent obtained, percent randomized	80%
Administration of vaccines in the vaccination group within 6 hours of randomization	60%
Administration of vaccines in the vaccination group within 12 hours of randomization	80%
Entire 48-hour monitoring period assessed for apnea events	80%

6.6.2 Full Study

6.6.2.1 Study Populations

[figure not shown]
We will define 3 study populations for the purpose of analyses.

1) Intent-to-treat (ITT) population

- Definition: The ITT population includes any infant that was enrolled and randomized in the study.

- **Analysis:** For the ITT analysis, study outcomes in the 48-hour monitoring after randomization will be evaluated in both vaccinated and unvaccinated group. Infants will be analyzed in their assigned treatment arms irrespective of receipt of vaccine.

[figure not shown]
Figure 3. Intent to Treat (ITT) Analysis

2) Modified intent-to-treat (mITT) population

- **Definition:** The mITT population includes any infant that was enrolled and randomized in the study.
- **Analysis:** For the mITT analysis, infants will be analyzed in their assigned treatment arms irrespective of receipt of vaccine. Study outcomes will be included in the analysis as follows:
 - **Vaccinated group:** study outcomes in the 48-hour monitoring after vaccination. If vaccination does not occur by 12 hours after randomization, then study outcomes will be assessed between 12 and 60 hours after randomization.
 - **Unvaccinated group:** study outcomes in the 48-hour monitoring period after randomization.

Figure 4. Modified Intent-to-Treat (mITT) Analysis

3) Per protocol (PP) population

- **Definition:** The PP population includes any infant that was enrolled, randomized and did not have any major protocol violations as determined by the study investigators.

- Analysis: For the per protocol analysis, study outcomes will be included in the analysis as follows:
 - Vaccinated group: study outcomes in the 48-hour monitoring after vaccination. The analysis will exclude infants who do not receive vaccine by 12 hours.
 - Unvaccinated group: study outcomes in the 48-hour monitoring period after randomization. The analysis will exclude infants who are vaccinated during the study period.

The mITT population will be the primary analysis population for all planned analyses for the study objectives. For comparison, pre-specified secondary analyses will also be performed using the ITT and PP populations. The ITT population will only be analyzed for the primary and secondary objectives. The PP population will be analyzed for all planned objectives as supporting analyses.

6.2.2.2 Interim Safety Data Review

Given that this study involves administering U.S.-licensed vaccines recommended by the ACIP for preterm infants and included as part of routine clinical care, there will not be a designated data safety monitoring board for this study. However, due to the fragility of the study population and interventional design, one interim safety data review will be performed with the goal of identifying unexpected safety concerns of clinical importance. The safety data review will provide the study the opportunity to identify unexpected safety concerns and make changes to the protocol if needed. The interim safety data review will be done by a safety monitoring panel with relevant expertise, comprised of experts who are not co-investigators on this study. The safety population for the interim safety review will include infants who were enrolled and randomized. Infants who participated in the pilot study will also be included. The safety monitoring panel will review clinical narratives of SAEs. If the CDC and study investigators determine additional analyses or reviews are needed, efforts will be made to conduct additional analysis or reviews that will not include analyzing the primary endpoint as a first step. This is to avoid introducing bias or increasing sample size needs for statistical power.

Enrollment will continue during the interim safety data review.

6.2.2.3 Final study analysis

A final analysis of the data will occur after all infants have completed the study and will include data from infants enrolled in the pilot study.

All proportions specified below in the objectives will be compared by group (unvaccinated group or vaccinated group) using a Mantel-Haenszel statistic in a stratified analysis by site (i.e. Duke, UNC and CCHMC) to control for the randomization blocks at the two-sided alpha 0.05 level unless otherwise specified. The odds ratio and corresponding 95% confidence interval will also be calculated and presented. There will be no adjustment to the alpha level made for the secondary and exploratory objectives.

Primary Objective 1 - To compare proportions of preterm infants with apnea in a 48-hour monitoring period after vaccination in the “vaccinated” group versus a 48-hour monitoring period after randomization in the “unvaccinated” group.

The proportion of infants with ≥ 1 apneic event apnea (as defined in Section A.5.3) will be presented for each group and compared using a Mantel-Haenszel statistic.

Secondary Objective 1 - To compare the clinical importance of apneic events in a 48-hour monitoring period after vaccination in the “vaccinated” group versus a 48-hour monitoring period after randomization in the “unvaccinated” group.

For this objective we will present the proportions of infants in each group who required increase in respiratory support (as defined in Section A.5.3) and compare these proportions using a Mantel-Haenszel statistic. We will also report summary statistics regarding the number of distinct episodes and the duration of episodes, including mean, median, standard deviation, interquartile range, and range. We will compare the number of distinct episodes of apnea and the duration of episodes between groups using the Wilcoxon rank sum test.

Secondary Objective 2 - To compare proportions of preterm infants with severe cardiorespiratory events in a 48-hour monitoring period after vaccination in the “vaccinated” group versus a 48-hour monitoring period after randomization in the “unvaccinated” group.

For this objective we will present the proportion of infants in each group experiencing a severe cardiorespiratory event (as defined in Section A.5.3) or received positive pressure ventilation at least once during the 48 hours after randomization/vaccination and compare these proportions using a Mantel-Haenszel statistic.

Exploratory Objective 1 - To compare proportions of preterm infants with temperature instability in a 48-hour monitoring period after vaccination in the “vaccinated” group versus a 48-hour monitoring period after randomization in the “unvaccinated” group.

For this objective we will present the proportion of infants the proportion of infants in each group experiencing fever and the proportion in each group experiencing hypothermia (as defined in Section A.5.3) at least once during the 48 hours after randomization/vaccination and compare these proportions using a Mantel-Haenszel statistic.

Exploratory Objective 2 - To compare proportions of preterm infants with other clinically important adverse events in a 48-hour monitoring period after vaccination in the “vaccinated” group versus a 48-hour monitoring period after randomization in the “unvaccinated” group.

For this objective we will present the proportion of infants the proportion of infants in each group experiencing other clinically important adverse events (as defined in Section A.5.3) at least once during the 48 hours after randomization/vaccination and compare these proportions using a Mantel-Haenszel statistic. We will repeat these analyses for serious adverse events. We will report SAE narratives and relatedness descriptions (see section 5.3).

Exploratory Objective 3 - To compare clinically important adverse events occurring between 48 hours and 14 days after vaccination among infants in the vaccinated group who do, and do not have apnea in a 48-hour monitoring period after vaccination.

For this objective we will present the proportion of infants in the vaccinated group with and without apnea in a 48-hour monitoring period who experience each of these clinically important adverse events (as defined in section A.5.3) at least once between 48 hours and 14 days after vaccination. These subgroup comparisons will be conducted a Fisher’s Exact Test at the alpha 0.05 level.

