2.1 Study Outcome Measures as Related to Objectives

Primary Outcome Measure (POM):

POM 1.1: Proportion of infants with ≥ 1 apneic event in a 48-hour monitoring period after vaccination in the “vaccinated” group and a 48-hour monitoring period after randomization in the “unvaccinated” group.

Secondary Outcome Measures (SOM):

SOM 1.1: Average number of apneic episodes in a 48-hour monitoring period after vaccination in the “vaccinated” group and a 48-hour monitoring period after randomization in the “unvaccinated” group.

SOM 1.2: Average duration of apneic episodes in a 48-hour monitoring period after vaccination in the “vaccinated” group and a 48-hour monitoring period after randomization in the “unvaccinated” group.

SOM 1.3: Proportion of infants requiring any increase in respiratory support in a 48-hour monitoring period after vaccination in the “vaccinated” group and a 48-hour monitoring period after randomization in the “unvaccinated” group.

SOM 2.1: Proportion of infants with ≥ 1 severe cardiorespiratory event in a 48-hour monitoring period after vaccination in the “vaccinated” group and a 48-hour monitoring period after randomization in the “unvaccinated” group.

SOM 2.2: Proportion of infants requiring positive pressure ventilation in a 48-hour monitoring period after vaccination in the “vaccinated” group and a 48-hour monitoring period after randomization in the “unvaccinated” group.

Exploratory Outcome Measures (EOM):

EOM 1.1: Proportion of infants with fever in a 48-hour monitoring period after vaccination in the “vaccinated” group and a 48-hour monitoring period after randomization in the “unvaccinated” group.

EOM 1.2: Proportion of infants with hypothermia in a 48-hour monitoring period after vaccination in the “vaccinated” group and a 48-hour monitoring period after randomization in the “unvaccinated” group.

EOM 2.1: Average number of oxygen desaturation events in a 48-hour monitoring period after vaccination in the “vaccinated” group and a 48-hour monitoring period after randomization in the “unvaccinated” group.

EOM 2.2: Average number of bradycardia events in a 48-hour monitoring period after vaccination in the “vaccinated” group and a 48-hour monitoring period after randomization in the “unvaccinated” group.

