All participants will have data captured from their continuous cardiorespiratory and pulse oximetry monitoring after randomization. Capture of continuous monitoring data will begin at randomization and end at 48 hours after vaccination (vaccinated group) or randomization (unvaccinated group). If infants in the vaccinated group are not vaccinated by 12 hours after randomization, capture of monitoring data will end at 60 hours after randomization. At the end of the 48-hour monitoring period, study staff at all enrolling sites will collect digital or printed output of data from cardiorespiratory monitors for all infants and send to the analysts at Duke University who will be blinded to the randomization group of the participants. To ensure the analysts are blinded to the treatment arms, the data obtained from the monitor for each infant will not include any personal or study identifiable information. Each output will be assigned a non-sequential coded number before they are sent to the analysts. The blinded analysis will interpret the output and record the date, time, and duration of each cardiorespiratory event (apnea, bradycardia, desaturation, and severe cardiorespiratory event) as defined below.

Procedures

[figure not shown]
Any procedures done as part of routine care (including, but not limited to, surgical procedures, eye exams, and central line placements) that occur beginning at randomization and ending at 48 hours after vaccination (vaccinated group) or randomization (unvaccinated group) will be recorded. Procedures occurring >60 hours after randomization in the vaccinated group will not be recorded. Data recorded will include the type of procedure, date/time of the procedure, length of the procedure, and a narrative describing any other important clinical information regarding the procedure.

Clinically important adverse events: days 1-2

Clinically important adverse events will be collected from randomization to 48 hours following randomization (unvaccinated group) or vaccination (vaccinated group). The following clinically important adverse events will be collected:

1. Apnea (*POM 1.1, SOM 1.1, SOM 1.2*)

- a. *Definition:* Apnea will be defined as a pause in respirations of >20 seconds, or a pause in respirations of >15 seconds with associated bradycardia (heart rate <80 beats per minute).
 - b. *Method of collection:* Obtained from the cardiorespiratory monitor as described above.
2. Increase in mode of respiratory support (SOM 1.3)

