## 1 INTRODUCTION

This document describes the statistical procedures that will be utilized for the CISA protocol Apnea in Preterm Infants Following the Administration of Routine Childhood Vaccines. This statistical analysis plan (SAP) describes the methods of statistical analysis. The SAP version 1.0 was written prior to any data being analyzed in order to avoid bias. Any subsequent changes that occur to the study protocol warranting changes to the analysis procedures will be documented in the SAP. **Table 1** below will be used for tracking changes to the SAP (both draft versions (0.X) and the final version (X.0)).

**Table 1.** Statistical Analysis Plan Versions

Version	Date of Approval	Major Changes from Prior Version
0.1	NA	Minor edits from [name]
0.2	NA	Minor edits from [name]
1.0	November 14, 2019	Not applicable
2.0	February 10, 2020	

• 6.4 Analysis population: Deleted analyzing secondary endpoints with ITT population

• 7.1: Presentation of baseline data: added postnatal age on the day of randomization and postmenstrual age on the day of randomization

• XXXX

• 8.4: Postmenstrual age evaluation (new section)

• Other minor edits

3.0	August 27, 2021	

• 9.0 Sensitivity Analysis: 1. Apneic events that cannot be adjudicated will be counted as non-apneic events

4.0	October 14, 2022	

• Change relative risk to odds ratio

• 8.4 Updated the PMA analysis to be performed by PMA group (PMA <37 weeks / ≥37 weeks)

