## 8.2 Secondary Objectives

There are two secondary objectives for this study.

- a) The first secondary objective (**SO-1**) is to compare the clinical importance of apneic events in a 48-hour monitoring period after vaccination in the “vaccinated” group versus a 48-hour monitoring period after randomization in the “unvaccinated” group.

There are 3 secondary outcome measures (SOM) for this objective. For SOM 1.1, the average number of apnea events in each group will be presented and the number of apnea events will be compared using a Poisson regression model with study site and gestational age as covariates to control for the randomization blocks. Summary statistics regarding the number of distinct apnea episodes and the duration of episodes, including mean, median, standard deviation, and range will be reported by group and site.

For SOM 1.2, the average duration of apnea episodes between groups will be compared using a mixed effects model (Robinson 2007) with a random intercept for each infant with one or more events and study site and gestational age as covariates to control for the randomization blocks. Apneic events will be identified using the same criteria for primary objective.

For SOM 1.3, the proportion of infants requiring an increase in respiratory support will be presented and compared using a Mantel-Haenszel statistic in a stratified analysis by site and gestational age to control for the randomization blocks at the two-sided  $\alpha 0.05$  level. The stratified odds ratio and corresponding 95% confidence interval for the occurrence will also be calculated. These tests will be performed at the  $\alpha 0.05$  level.

Increase in mode of respiratory support will be defined as (a) progression from any lower level at baseline (at time of randomization in the unvaccinated group and vaccination in the vaccinated group) to any higher level, as well as (b) any increase in nasal cannula flow rate, or continuous positive airway pressure (CPAP).

- b) The subsequent secondary objective (**SO-2**) is to compare proportions of preterm infants with severe cardiorespiratory events in a 48-hour monitoring period after vaccination in the “vaccinated” group versus a 48-hour monitoring period after randomization in the “unvaccinated” group.

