#### **8.4 Postmenstrual age (PMA) Evaluation**

Study objectives PO1, SO1, SO2, EO2.1, EO2.2, EO3.1, and EO3.2 will be presented and evaluated between groups by postmenstrual age group (PMA <37 weeks /  $\geq$ 37 weeks). PMA will be defined as the sum of gestational age plus postnatal age. PO1, SO2, and EO3 are categorical with either no event or 1 or more events, and will be presented and compared using a Mantel- Haenszel statistic by PMA group at the two-sided alpha 0.05 level. The stratified odds ratio and corresponding 95% confidence interval for the occurrence will also be calculated. SO1 and EO2 are count data and will be compared using a Poisson regression model with study site as covariates by PMA group. These tests will be performed at the alpha 0.05 level.

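### Protocol and SAP name different tests for apnea count (SOM 1.1) and duration (SOM 1.2), with no stated precedence; the protocol's duration test lacks a unit of analysis and the SAP's count model ignores overdispersion

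*Protocol*

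**What the plan says.** Protocol 6.2.2.3, Secondary Objective 1, covers both outcomes in one sentence: "We will compare the number of distinct episodes of apnea and the duration of episodes between groups using the Wilcoxon rank sum test". It names no strata for this test and does not say whether duration is analysed per episode or per infant.

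SAP 8.2 treats the outcomes separately. For SOM 1.1, "the number of apnea events will be compared using a Poisson regression model with study site and gestational age as covariates". For SOM 1.2, "the average duration of apnea episodes between groups will be compared using a mixed effects model", specified "with a random intercept for each infant with one or more events and study site and gestational age as covariates". No robust variance, scale parameter or other allowance for overdispersion is stated for the Poisson model.

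Two further passages bear on the unit of analysis. Protocol 5.4 has the blinded readers "record the date, time, and duration of each cardiorespiratory event", so one infant can supply several durations. Protocol 2.1 defines the outcome as "SOM 1.2: Average duration of apneic episodes in a 48-hour monitoring period after vaccination", which does not settle whether the average is taken over infants or over episodes.

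SAP 8.4 repeats the Poisson choice for subgroups by postmenstrual age: "SO1 and EO2 are count data and will be compared using a Poisson regression model with study site as covariates by PMA group".

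**The concern.** The two documents would produce different results for the same outcomes. A rank test addresses a shift in distribution. The Poisson model estimates a ratio of mean counts, and the mixed model a difference in mean duration. The SAP models adjust for site and gestational age, the randomization strata, while the protocol's test does not. With no precedence rule, whoever runs the analysis has two prespecified answers to choose from, at an unadjusted alpha of 0.05.

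Each document also has a weak point. If the protocol's test pools episodes, an infant with ten episodes counts as ten independent observations. If the SAP's Poisson model is fitted as written, it assumes that the variance of the infant counts equals their mean. Apnea recurs within some infants and is absent in most, so the variance is likely to be larger. Secondary Objective 1 is the trial's evidence on how much any apnea matters clinically, and a false positive there could be read as vaccine-related harm.

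**Working it through.** **1. The plan's own figure.** The only power statement (protocol 6.5, SAP 4.2) concerns the primary outcome: 15% vs 30%, 135 per group, two-sided 0.05.
- Pooled proportion 0.225; null SE = √(2 × 0.225 × 0.775 / 135) = 0.0508; alternative SE = √((0.1275 + 0.21) / 135) = 0.0500.
- Power = Φ((0.15 − 1.96 × 0.0508) / 0.0500) = Φ(1.008) = 84.3%.
- 270 / 0.9 = 300.

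These figures reproduce, but they say nothing about SOM 1.1 or 1.2, for which the plan gives no figures.

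**2. The passages side by side.**

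| Outcome | Protocol 6.2.2.3 | SAP 8.2 |
|---|---|---|
| SOM 1.1, count | Wilcoxon, no strata stated | Poisson, site and gestational age |
| SOM 1.2, duration | Wilcoxon, no strata, unit not stated | Mixed model, random intercept per infant, site and gestational age |

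**3. Duration under no effect.** From the plan: 135 × 0.15 ≈ 20 and 135 × 0.30 ≈ 40 infants with apnea. Assumed, because the documents do not give them: geometric numbers of episodes with mean m, and within-infant correlation ρ. Model: duration = uᵢ + eᵢⱼ, with var(u) = ρ and var(e) = 1 − ρ. The table shows the rejection rate at nominal 5% for Wilcoxon on pooled episodes (2,000 runs each, Monte Carlo SE 0.4 to 1.1 points).

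| m | ρ = 0 | ρ = 0.1 | ρ = 0.2 | ρ = 0.4 |
|---|---|---|---|---|
| 1 | 5% | 5% | 5% | 5% |
| 2 | 4% | 6% | 10% | 14% |
| 3 | 5% | 10% | 13% | 21% |
| 6 | 4% | 16% | 24% | 36% |

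Other runs of the mildest clustered setting (m = 2, ρ = 0.1) gave 6.7% and 7.5%, hence about 7%. Wilcoxon on one mean per infant gave 4% to 5.5% in every cell. A second design had 135 per arm, equal proportions affected (15% to 30%), m = 2 to 8 and ρ = 0.1 to 0.5. It gave 7% to 48% for pooled episodes and 4% to 5.5% for infant means.

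**4. Counts under no effect.** 135 infants per arm, 15% with any apnea in both arms. Counts are gamma-Poisson with dispersion k (assumed). The mean μ solves (1 + μ/k)^(−k) = 0.85, so μ = k(0.85^(−1/k) − 1), and variance/mean = 1 + μ/k. The plain Poisson test is z = ln(S₁/S₀) / √(1/S₁ + 1/S₀), where S is the arm's total count. The robust version replaces the variance with Σ(y − ȳ)²/S² summed over arms. No covariates; 4,000 runs each.

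| k | μ | variance/mean | Plain Poisson | Robust Poisson | Wilcoxon on infant counts |
|---|---|---|---|---|---|
| 0.1 | 0.408 | 5.08 | 38% | 7% | 5% |
| 0.3 | 0.216 | 1.72 | 13% | 6% | 5% |
| 1.0 | 0.176 | 1.18 | 7% | 5% | 5% |

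Repeat runs gave 37% to 38%, 12% to 13% and 6% to 7% for plain Poisson, and 5% to 7.5% for robust Poisson at the two smaller values of k. A different count model fixed the share of infants affected at 15% or 22.5%. There, plain Poisson rejected 13% to 14% with a mean of 1.5 episodes per affected infant, 22% to 25% with 2, and 44% with 4 (15% affected only). Wilcoxon stayed at 4% to 6%. With exactly one episode per affected infant, plain Poisson was conservative at 2% to 3%.

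**The case against.** The strongest reply is that the SAP is the operative analysis document. Its introduction says that it sets out the procedures to be used, and that version 1.0 was written before any data were analysed. It gives one specific method per outcome, and its random intercept handles repeated episodes. This largely stands for SOM 1.2. A reader might infer from the mismatch that the two outcomes have no valid analysis at all, and the documents do not support that. The SAP's model for SOM 1.2 accounts for clustering, and the protocol's rank test is sound for SOM 1.1, where each infant has one count. What is missing is an express rule on which document prevails.

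A second reply is that the protocol never says episodes are pooled. That is correct. Pooling is the natural reading of a test on episode durations that are recorded event by event, but the outcome is an average duration, so one mean per infant is also possible. It would therefore be too strong to state as fact that the protocol treats episodes as independent.

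A reader might also see an undocumented change of method, because the SAP says "Any subsequent changes that occur to the study protocol warranting changes to the analysis procedures will be documented in the SAP" and its version table does not mention these tests. That does not follow. The table records changes between SAP versions, and if version 1.0 already contained these models there was nothing to list.

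Finally, the monitor output is read by blinded analysts, so the open-label design does not bias event detection by those readers. This stands, but it does not settle the choice between two tests.

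**Conclusion.** The documents conflict on the tests for SOM 1.1 and SOM 1.2, and the supplied text does not resolve the conflict. That part needs no assumption.

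The sizes are conditional. For SOM 1.2, pooled episodes give about 7% to 36% false positives for 2 to 6 episodes per infant and correlation 0.1 to 0.4. The rate stays near 5% with one value per infant, one episode per infant or zero correlation. For SOM 1.1, plain Poisson gives about 12% to 38% at dispersion 0.3 and 0.1, and 6% to 7% at dispersion 1. Neither episode numbers, correlation nor dispersion is given in the documents, and the simulations used normal-scale durations and no covariates.

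It is tempting to conclude that the protocol should simply adopt the SAP methods. That is right for SOM 1.2. For SOM 1.1 it would put the less reliable of the two tests in charge. The primary analysis and the sample size are unaffected.

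**What to change.** Before the groups are compared on these outcomes:

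1. **SOM 1.2.** In protocol 6.2.2.3, replace the Wilcoxon test of duration with the SAP's random-intercept model, and state that SAP 8.2 governs.
2. **SOM 1.1.** Name one analysis in both documents. Keep site and gestational age as covariates, and use either Poisson regression with robust (sandwich) variance or a negative binomial model. Robust variance was still slightly liberal (about 7%) in the most overdispersed setting.
3. **Rank test, if kept.** Make it a named sensitivity analysis with one value per infant, stratified by site and gestational age (van Elteren).
4. **SAP 8.4.** Carry the SOM 1.1 choice into the subgroup section, and correct its description of SO 1 as count data, since SO 1 also contains a duration (SOM 1.2) and a proportion (SOM 1.3).

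The cost is wording in both documents and one optional analysis. No extra data or infants are needed.
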